Following completion of these tests, subjects will be randomized (using a table of random numbers) to receive, in open label fashion, one of the following treatment regimens: (i) Group I will be started on pioglitazone (15 mg/day) plus metformin (1000 mg/day) with the supper meal and exenatide (5 mcg s.c. bid 30 min before breakfast and supper) and up-titrated to 45 pioglitazone plus 2000 metformin and 10 mcg s.c. bid exenatide to achieve HbA1c <6.0%; (II) Group II will be started on metformin, 1000 mg with breakfast and 1000 mg with supper, glyburide and basal insulin will be added and up titrated to achieve HbA1c <6.0% Subjects will be recruited during the first year and followed up for additional two years. After completing the repeat studies, subjects will be asked to continue in the study and with the study medications without any change. Follow up visits will occur every 3 months) until the last patient recruited into the study completes 2 –years of follow-up. At the Follow visit Fasting Glucose and HbA1C will be performed. At the annual visits blood work to check the following: fasting glucose, HbA1C, and other repeat labs. Every 2 years or if the subject decides to discontinue participation, we will repeat the annual labs, OGTT, eye photographs, and carotid ultrasound.

4. Study Population(s).

You will be drawing subjects from one or more populations. In medical research, for example, a population can be individuals with type 2 diabetes controlled with diet, or a population of healthy individuals. In social behavioral research, a population can be individuals attending an education program, etc.

- a. How many different populations are you enrolling in this study?
- b. For each different population, provide a short descriptive label: (e.g., *normal-healthy, diabetics, patients needing surgery, parents, child, etc.*)

1

720 Newly diagnosed type 2 diabetic subjects
Will be enrolled to have 600 completers .

For each **specific** population identified 4b, provide the following information in the table provided below. (**One table is provided, use copy and paste for additional tables if enrolling more than one population.**)

Population # [Type # given to population in 4b]	Population Descriptive Label: [Insert short label from 4b] Enrollment of [Insert #] requested to obtain [Insert #] completers.
XCheck here if enrolling only one population	
(1)	Identify the criteria for inclusion :

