If, at any time after achieving a HbA_{1C} $\leq 6.0\%$, the HbA_{1C} rises above 6.0% and the subject is on submaximal doses of metformin or pioglitazone or exenatide, the medication(s) will be titrated up to the maximally effective dose and the subject will not be considered a treatment failure.

If, after month six, the HbA_{1C} $\geq 6.0\%$ and the subject is on maximum doses of all triple therapy medications, the subject will be considered a treatment failure. If, after month 6, the HbA_{1C} rises to $> 6.5\%$, bedtime glargine insulin (10-20 units) will be started and titrated to a maximum of 60 units to achieve a FPG < 110 mg/dl and HbA_{1C} $< 6.0\%$. If more than 60 units of glargine insulin is required to reduce the HbA_{1C} $< 6.5\%$, regular insulin will be added to each meal and adjusted based upon the pre- and post-meal blood glucose levels. These "treatment failure" subjects will continue with all follow up visits/procedures. Throughout the titration process, downward adjustments will be allowed for the development of hypoglycemia, as defined by a blood glucose less than 60 mg/dl with (symptomatic hypoglycemia) or without (asymptomatic hypoglycemia) symptoms. Serious hypoglycemia is defined as any hypoglycemic reaction requiring assistance from a third party for recovery.

GROUP II: Group II will be started on metformin, 1000 mg with breakfast and 1000 mg with supper.

If, after month one, the FPG ≥ 110 mg/dl or HbA_{1C} $\geq 6.0\%$, glipizide (5 mg) will be added: 1-2 tablets with breakfast depending on the FPG, HbA_{1C}, and discretion of the investigator in order to avoid hypoglycemia.

If, after month two, the FPG ≥ 110 mg/dl or HbA_{1C} $\geq 6.0\%$, the glipizide dose will be increased to 4 tablets (20 mg/dl).

If, after month three, the FPG > 110 mg/dl or HbA_{1C} $> 6.0\%$, bedtime basal insulin (10-20 units) will be started and titrated up to achieve a FPG < 110 mg/dl or HbA_{1C} $< 6.0\%$

If, at any time after achieving a HbA_{1C} $< 6.0\%$, the HbA_{1C} rises above 6.0% and the subject is on submaximal doses of metformin or glipizide or glargine insulin, the medication(s) can be titrated up to the maximally effective dose and the subject will not be considered a treatment failure.

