If, after month six, the HbA_{1C} $> 6.0\%$, and the subject is on maximum doses of metformin, glipizide, and glargine insulin, the subject will be considered a treatment failure. Regular insulin will be added to each meal when the HbA_{1C} rises to $> 6.5\%$ and adjusted based upon the pre- and post-meal blood glucose levels. These "treatment failure" subjects will continue with all follow up visits/procedures.

Throughout the titration process, downward adjustments will be allowed for the development of hypoglycemia, as defined by a blood glucose less than 60 mg/dl with (symptomatic hypoglycemia) or without (asymptomatic hypoglycemia) symptoms. Serious hypoglycemia is defined as any hypoglycemic reaction requiring assistance from a third party for recovery.

Following their enrollment into the study, all T2DM participants will return to the Clinical Research Center (CRC) at the TDI for follow up visits every 3 months. Telephone calls also will be made to each participant every 6 weeks. During the telephone/CRC visits, subjects will be asked questions about interim medical history, home glucose monitoring results, and compliance with the medical regimen.

During each 3-month follow-up visit to the CRC, body weight, waist circumference (Gulick III tape measure), and blood pressure (Dynamap) will be measured. Blood will be drawn for FPG and HbA_{1c}, and pharmacological therapy will be adjusted based on the HbA_{1c}, FPG, and HBGM results (see prior algorithm). Plasma lipids and 24-hour urine albumin excretion will be measured annually or more frequently as indicated by test results. In addition to glycemic control, all subjects will receive therapy for any abnormal cardiovascular risk factors: hypercholesterolemia (goal LDL <100 mg/dl), hypertriglyceridemia (goal <150 mg/dl), hypertension (goal <130/80 monthly), albumin excretion (goal < 30 mg/day). At the end of three years, the OGTT, DEXA, fundus photography, 24 hour urine for albumin, hyperglycemic clamp, ankle-arm blood pressure, and carotid IMT will be repeated.

Primary End Point: The primary end point of the study is the difference in HbA_{1c} between Group I (triple combination therapy at time of initial diagnosis) and Group II (stepwise therapy).

Secondary End Points: The following parameters will be measured as secondary endpoints;

- 1) Number of subjects in each group with HbA_{1c} < 6.0%

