
The results of this study will provide a novel, more progressive therapeutic approach to the treatment of T2DM, based upon correction of known pathogenic abnormalities responsible for the disease.

Data Analysis and Statistical Methods

Values are presented as mean \pm SEM. Two-sided t test was used to compare mean differences between treatment arms, and the χ^2 test was used to test the significance of discrete variables. The Cox proportional hazards model was used to estimate the influence of therapy on failure to maintain the treatment goal. The model was adjusted for other confounders (namely, age, sex, BMI, disease duration, and baseline HbA1c level).

Sample size calculation:

The study was powered to detect a 0.5% (60.95 SD) HbA1c difference between the two treatment arms based on the HbA1c decrease in the PROactive study (22). We calculated that 76 patients who completed the study would be required in each arm to detect significant difference between the two groups at $\alpha = 0.05$. A detailed description of the sample size

calculation is given in the Supplementary Material.

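### A single unconfirmed HbA1c at the titration target can label a maximum-dose subject a treatment failure; if the Cox model uses this rule, measurement noise can create false first events

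*Combined protocol and SAP*

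**What the plan says.** Section 6a gives each arm a failure rule. Group I's begins "If, after month six, the HbA_{1C} $\geq 6.0" percent, and continues "and the subject is on maximum doses of all triple therapy medications, the subject will be considered a treatment failure". Group II's begins "If, after month six, the HbA_{1C} $> 6.0" percent, and continues "and the subject is on maximum doses of metformin, glipizide, and glargine insulin, the subject will be considered a treatment failure". Neither asks for a repeat measurement. A high value on submaximal doses is not a failure; in Group I, "the medication(s) will be titrated up to the maximally effective dose and the subject will not be considered a treatment failure".

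Section 3 sets the same target in both arms. Group I is started low "and up-titrated to 45 pioglitazone plus 2000 metformin and 10 mcg s.c. bid exenatide to achieve HbA1c <6.0" percent; in Group II, "glyburide and basal insulin will be added and up titrated to achieve HbA1c <6.0" percent. No lower bound is given. HbA1c is read every three months.

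The analysis section states: "The Cox proportional hazards model was used to estimate the influence of therapy on failure to maintain the treatment goal". It does not define that event, and other parts of the document offer several candidates:

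- Section 1 (objective 1) and the Background tie achieving and maintaining control to HbA1c below 6.5%.
- The Abstract sets the goal at below 6.0%.
- Secondary endpoint 2 needs HbA1c above 6.0% and the addition of mealtime insulin.
- Section 7 (item 7) calls a subject a failure when A1c stays above 8% on full doses.

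**The concern.** When the failure cut-off equals the treatment target, a subject who is controlled slightly below target can be carried over the line by assay and biological variation alone. Every quarterly visit is another chance, and a time-to-first-event analysis keeps the first crossing whatever follows. Durability is in the trial's title, a lower rate of therapeutic failure is one of the Abstract's hypotheses, and this is the only outcome given a Cox model. False first events would overstate failure in the affected arm, date it too early and distort the hazard ratio.

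The arms also differ at the boundary. Group I fails at 6.0% or more, Group II only above 6.0%. In Group I, a value of exactly 6.0% satisfies both the wording for having achieved the goal (6.0% or less) and the wording for failure.

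**Working it through.** **The plan's own figure.** The only sample-size calculation is for the HbA1c difference: 0.5 points, SD 0.95 (the printed 60.95 read as ±0.95), two-sided alpha 0.05. Power is not stated. At 90%, n = 2 × (1.960 + 1.282)² × 0.95² / 0.5² = 75.9, so 76 per arm, as stated. It does not bear on the failure rule, for which the documents give no measurement error or expected event count.

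**Inputs.** Cut-off 6.0% (Section 6a). Number of visits k after month six: 10 for months 9–36 (tests repeated at three years, Section 6a), or 6 for months 9–24 (two-year follow-up, Abstract). Assumptions: within-subject SD s of 0.10, 0.15 or 0.20 points; constant true level m; independent errors; maximum doses throughout.

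**Formulas.** Per visit, p = 1 − Φ((6.0 − m)/s). One value: 1 − (1 − p)^k. Two consecutive values: let a be the probability of being unlabelled with the last value low, and b unlabelled with the last value high. At each visit a' = (a + b)(1 − p), b' = a·p, and b·p is added to the failures.

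**Stable true HbA1c of 5.8%.** The distances to the cut-off are 2, 1.33 and 1 SD, so p = 0.0228, 0.0912 and 0.1587.

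| SD | one value, k = 10 | two consecutive, k = 10 | one value, k = 6 |
|---|---|---|---|
| 0.10 | 21% | 0.5% | 13% |
| 0.15 | 62% | 7% | 44% |
| 0.20 | 82% | 18.5% | 65% |

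**Other true levels, k = 10, SD 0.10 / 0.15 / 0.20, one value.** 5.5%: below 0.1 / 0.4 / 6%. 5.7%: 1.3 / 21 / 50%. 5.9%: 82 / 95 / 98%. With two consecutive values, 5.9% still gives 18.5 / 39 / 52%, so confirmation reduces the problem but does not remove it very close to the cut-off.

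**Effect on the hazard ratio.** Illustration: true failure hazards 0.10 and 0.20 per year (HR 0.50), true HbA1c 6.4% after failure, the same stable level and a cut-off of 6.0% or more in both arms, k = 10, HR taken as the ratio of events per person-year.

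| Stable level | Rule | SD 0.10 | SD 0.15 | SD 0.20 |
|---|---|---|---|---|
| 5.75% | one value | 0.56 | 0.74 | 0.85 |
| 5.75% | two consecutive | 0.51 | 0.52 | 0.58 |
| 5.5% | one value | 0.51 | 0.51 | 0.56 |

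**Share of events that are false.** In assumed populations (mean 5.5–5.8%, between-subject SD 0.3, mean drift 0–0.2 points a year with SD 0.1, the same noise SDs), about 6% to 63% of single-value events fall in subjects whose true value never reached 6.0%. With two consecutive values the range is about 1% to 31%.

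**Unequal inequalities.** If HbA1c is reported to 0.1, Group I fails from an underlying reading of 5.95 and Group II from 6.05. At a true 5.8%, SD 0.15 and k = 10, p is 0.159 and 0.048, giving 82% and 39%.

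**If the event were 6.5%.** At a true 5.9% and SD 0.20, noise crosses 6.5% with probability 1.3% over 10 visits; at 5.8% it is 0.2%.

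**The case against.** The strongest reply is that the Cox event is not stated to be this rule. The objectives and Background attach maintenance of control to 6.5%, where noise crossings are negligible. The listed failure endpoint also requires mealtime insulin: in Group II this starts above 6.5%, and in Group I only after more than 60 units of glargine are needed. A stable subject at 5.8% would hardly ever meet either. This stands, and it makes the point conditional. It does not remove it: the Abstract gives 6.0% as the goal, and the Section 6a rules are the only post-month-six failure rules built on that number alone.

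A reader might infer that subjects are held just under 6.0% and that noise therefore makes many of the failures. The documents do not support that. The target has no floor, fasting glucose also drives titration, and no on-treatment distribution is given. At 5.5% the effect is slight.

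A reader might also infer that failure status is permanent, or that false events are equal by arm and pull the hazard ratio towards 1. The text never calls the status permanent; that would follow only from a first-event analysis. Equal rates do not follow either, because the inequalities differ, subjects on submaximal doses cannot fail, downward dose adjustment is allowed, and Group II has no stated glargine maximum, so when its rule can apply is unclear. The illustration above puts every subject at maximum dose with one cut-off, which simplifies in the same way.

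**Conclusion.** The concern holds in a limited form. Section 6a classifies failure on one unconfirmed HbA1c at a cut-off equal to the treatment target. If the Cox model uses that rule, false first events are likely for maximum-dose subjects whose true level is about 5.7–5.9%, and unlikely for those near 5.5%. Whether they form a small or a large part of all events cannot be settled from the documents: the size rests on an assumed SD of 0.10–0.20 points and assumed true levels, and the direction of bias between arms is uncertain. The primary HbA1c comparison is not touched, and secondary endpoint 2 or an event set at 6.5% would be largely unaffected. The change is still worth making because it is cheap and concerns the trial's durability outcome.

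**What to change.** For endpoint classification only:

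1. State which event the Cox model uses, and reconcile Section 1, the Background, the Section 6a failure rules, secondary endpoint 2, Section 7 item 7 and the Abstract.
2. Use the same inequality in both arms.
3. If the 6.0% cut-off is used, count a failure when two consecutive scheduled HbA1c values meet it on maximum doses, dated to the first. State how a missing next value is handled.
4. Count a single value above 6.5% as confirmed in both arms. Both algorithms already add insulin at that level, which could otherwise bring the next value down and hide a true failure. The insulin step itself should not serve as confirmation: it is an open-label decision and a different step in each arm.
5. Report the single-value version as a sensitivity analysis.

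The analysis section is written in the past tense. If the Cox analysis has already been run, the confirmed version should be labelled post hoc and shown beside it.

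The cost is wording and programming. The confirming value is the next quarterly HbA1c, so no visit is added, and no treatment step changes or waits for it. The downside is fewer events, and a crossing between 6.0% and 6.5% at the last visit remains unconfirmed.

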Type 2 diabetes mellitus (T2DM) is a common metabolic disease that affects 21 million Americans and is associated with significant morbidity and mortality secondary to micro- and macrovascular complications. Subjects with T2DM manifest insulin resistance in skeletal muscle, liver and adipocytes and impaired insulin secretion. Although many therapeutic agents have been developed to target the pathogenic abnormalities in subjects with T2DM, the current ADA recommendation for pharmacological therapy in T2DM remains based on monotherapy, with dose escalation, followed by sequential addition of oral antidiabetic agents and eventually insulin to control blood glucose levels. Unfortunately, the majority of type 2 diabetic individuals in the US fail to achieve the recommended level of glycemic control ($\text{HbA}_{1c} < 6.0\%$) using this approach. In this study, I propose to explore the efficacy of a novel therapeutic approach to attain glycemic control in T2DM subjects. This novel approach is based upon the initiation of triple combination therapy at the time of diagnosis with agents that target specific pathogenic abnormalities present in T2DM. Two groups of newly diagnosed, drug naive T2DM subjects will be studied: (i) Group I will receive triple combination therapy with metformin, pioglitazone, and exenatide as initial therapy; (ii) Group II will be started on metformin monotherapy followed by sequential addition of a sulfonylurea and then glargin insulin. The goal of therapy in both groups is to reduce the $\text{HbA}_{1c} < 6.0\%$. Subjects will be recruited over one year and followed for 2 years (total study duration =3 years). The primary outcome will be the difference in HbA_{1c} between Groups I and II. Secondary outcomes will include failure to achieve the glycemic goal ($\text{HbA}_{1c} < 6.0\%$), improvements in insulin resistance, beta cell function, markers of inflammation, markers of oxidative stress, and carotid intima media thickness. I hypothesize that subjects started on combination therapy at the time of diagnosis of T2DM will have better and more durable glycemic control, a lower rate of therapeutic failure, enhanced insulin sensitivity, and improved/preservation of beta cell function compared to subjects receiving the “conventional” ADA-recommended stepped-therapeutic approach with “standard” medications. I also hypothesize that subjects started on initial combination therapy will have: (i) lower levels of inflammatory markers and (ii) reduced carotid IMT. On a long-term basis, one would expect the superior metabolic control in T2DM who receive aggressive combination therapy from onset to have a lower rate of diabetic complications.

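### The Group II basal insulin target can be met on fasting glucose alone with HbA1c still at or above 6.0%, against that arm's own start trigger, the stated goal and the joint target used for Group I

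*Combined protocol and SAP*

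**What the plan says.** Section 6a sets out the Group II algorithm. The insulin step opens with "If, after month three, the FPG > 110 mg/dl or" an HbA1c above 6.0%. The target then reads "bedtime basal insulin (10-20 units) will be started and titrated up to achieve a FPG < 110 mg/dl or" an HbA1c below 6.0%. Trigger and target are both either/or statements.

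Three other places bear on the target:

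- **Section 3, Study Design, Group II:** "glyburide and basal insulin will be added and up titrated to achieve HbA1c <6.0"%. No FPG alternative is given.
- **Abstract:** "The goal of therapy in both groups is to reduce the" HbA1c to below 6.0%.
- **Section 6a, Group I:** glargine "will be started and titrated to a maximum of 60 units to achieve a FPG < 110 mg/dl and" an HbA1c below 6.0%, so both conditions must hold.

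Section 6a also makes the between-group difference in HbA1c the primary endpoint, and lists the number of participants with HbA1c below 6.0% first among the secondary endpoints. Treatment is open label.

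**The concern.** A dose target tells the investigator when to stop raising the dose. If either of two abnormalities starts a drug, the matching target is that both have resolved. Here a participant can start basal insulin because HbA1c is too high and meet its target the same day because FPG is acceptable. Nothing in that sentence then requires an increase above the starting 10-20 units.

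This is an operative dosing rule in one arm, and it acts on the variable that is the primary endpoint. Taken alone, permission to stop on FPG can only leave Group II HbA1c equal to, or higher than, what an HbA1c target would give. A reader of the result would want to know whether participants were in fact held at that point.

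**Working it through.** The plan gives no figure to reproduce here, and the sample size does not enter. The check compares the start rule with the target, using one value on each side of each threshold.

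**Inputs (Section 6a, Group II).** Start: FPG >110 or HbA1c >6.0%. Target as written: FPG <110 or HbA1c <6.0%. Joint target, as for Group I glargine: FPG <110 and HbA1c <6.0%. Goal (Section 3 and Abstract): HbA1c <6.0%.

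| FPG (mg/dl) | HbA1c (%) | Starts insulin | Target as written met | HbA1c goal met | Joint target met |
|---|---|---|---|---|---|
| 115 | 6.4 | yes | no | no | no |
| 115 | 5.9 | yes | yes | yes | no |
| 105 | 6.4 | yes | yes | **no** | no |
| 105 | 5.9 | no | yes | yes | yes |

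Three of the four states start insulin. Under the rule as written, 1 of these 3 (FPG 105, HbA1c 6.4%) counts as at target while above the HbA1c goal. Under the joint target it is 0 of 3. These are logical states, not patients. At HbA1c exactly 6.0% with FPG 105, the start trigger is not met; for someone already on insulin, though, the written target is met and the goal is not.

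The second row shows why the joint target needs a qualifier. At FPG 115 and HbA1c 5.9% it would call for more insulin in someone already at the HbA1c goal.

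**Does other text restore the HbA1c target?**

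1. *Later re-titration, Group II.* It applies only after HbA1c below 6.0% has been reached, and it is permissive: "the medication(s) can be titrated up to the maximally effective dose". It misses anyone who never got there.
2. *Three-monthly adjustment.* This uses HbA1c, FPG and "HBGM results (see prior algorithm"), so it points back to the same rule.
3. *Section 7, item 7.* Therapy is adjusted if control is inadequate, but no threshold is given below the HbA1c >8% on full doses that returns a participant to usual care.
4. *Mealtime insulin.* Section 6a adds regular insulin in Group II when HbA1c rises above 6.5%, with no FPG condition. Read on its own, this limits the unaddressed range to HbA1c 6.0-6.5% with FPG <110. The neighbouring sentences, however, concern participants who have failed on maximum doses. If it covers only them, a participant stopped on FPG at a submaximal dose is neither escalated nor counted as a failure under that definition, and the gap extends above 6.5%.

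**Is there a stated safety reason for the softer target?** Hypoglycemia is given as a ground for "discretion of the investigator in order to avoid hypoglycemia" at the glipizide step, and as a reason for downward adjustment at any time. It is not given as the reason for this target.

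**The case against.** The strongest reply is that this is a one-word slip. Section 3 and the Abstract state the goal plainly, a participant at FPG 105 and HbA1c 6.4% still receives 10-20 units, and the trigger after month three has no end date, so HbA1c above 6.0% can prompt action at any later visit. Much of this is fair. Investigators may well have titrated to HbA1c. But nothing written required them to, and a repeated trigger leads back to a target that is already met.

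A second reply is safety. An HbA1c-only stopping rule would keep raising bedtime insulin in someone with a low-normal fasting glucose. Group II has no 60-unit cap, and downward adjustment is tied to glucose below 60 mg/dl. This stands, and it shapes the fix.

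A third reply is that little remains to change. The Washout Phase ends this algorithm at year 6: therapy stops if HbA1c is below 7.5%, and Group II participants above that level switch to triple therapy. The protocol's approval date is in 2019 and the analysis text is in the past tense. This also stands, so the rewording may reach few participants.

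A reader might infer that the rule biases the trial toward Group I. The documents do not support that. The two insulin steps are not like for like: in Group II insulin is part of the assigned regimen, while in Group I glargine is a rescue. Group II insulin starts earlier (after month three rather than month six) and at a lower HbA1c (above 6.0% rather than 6.5%). It also has FPG as a separate trigger and no 60-unit cap. All four features push the other way.

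**Conclusion.** The inconsistency is real and should be corrected. As written, Group II basal insulin may stop on FPG below 110 mg/dl with HbA1c at or above 6.0%, contrary to the arm's start trigger, the stated goal and the Group I glargine target.

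One of the three starting states is affected, and none would be under a joint target. The HbA1c range left without required action is 6.0-6.5% if the mealtime insulin sentence stands alone, and wider if it covers only maximum-dose failures. The documents do not settle which.

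Taken alone, the rule's effect on Group II HbA1c is zero or upward. The share of participants affected, the arm-level size and the net direction across the two algorithms cannot be determined. A reader might take one state in three to mean a third of Group II, or conclude that HbA1c went wholly unchecked. Neither follows: the first is a count of logical states, and the second overlooks the mealtime insulin rule. The conclusion rests on reading the target sentence literally.

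**What to change.** Change the Group II target in Section 6a to *FPG <110 mg/dl and HbA1c <6.0%*, with three conditions:

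- no basal increase is required once HbA1c is below 6.0%;
- no further basal increase is made once fasting glucose reaches a stated lower limit or hypoglycemia occurs (the documents give no such limit, so the investigators must set one);
- the existing downward adjustment for hypoglycemia stays.

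This agrees with Section 3, the Abstract and the Group I wording, and does not push insulin on someone at FPG 115 and HbA1c 5.9%. The same edit should say whether the mealtime insulin rule above 6.5% applies to all Group II participants or only to those who have failed on maximum doses.

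The rewording reaches only Group II participants still on the algorithm before the year-6 washout; the documents do not say how many there are. For those already treated, where dose records exist, tabulate by arm the participants on basal insulin with FPG <110 mg/dl and HbA1c at or above 6.0% whose dose was not raised, and report this with the primary result. FPG and HbA1c are already measured every 3 months, but the documents do not describe insulin dose records.

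The cost is an edit to one part of the algorithm and one table. The downside is somewhat more insulin and hypoglycemia risk in Group II, where the risk table in Section 6c already lists hypoglycemia as likely (more than 20 per 100).
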